Aim 2. To pilot test the mindEMI among cancer survivors. We will obtain feedback from another 10 survivors who will pilot the prototype of mindEMI that will deliver the MBI in real-time at both random moments and when high levels of smoking vulnerability are self-reported via EMA. The primary outcomes will be participants' open-ended feedback along with perceived utility and likability of the mindEMI and retention through the end of treatment.

This novel cessation intervention and demonstration of key feasibility and acceptability benchmarks, combined with the focused training plan, will lead to a future R01 trial of mindEMI for smoking cessation tailored for survivors. Ultimately, the intervention will dismantle cancer-specific and general risk factors of smoking relapse, with high accessibility, scalability, and the ability to intervene in real-time, thus increasing effect.

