4.2.2. Aim 2: Procedure and Data Collection

Aim 2 will be conducted remotely. Importantly, the mindEMI content will comprise brief mindfulness strategies and meditations selected and/or modified *per survivors' feedback* from Aim 1 and EMA items will assess *both cancer-specific and general smoking relapse vulnerabilities* by including psychometrically sound items including cancer-specific items.⁸⁸⁻⁹¹ Thus, the prototype will be adapted specifically to survivors.

PI: [name]

Study participation will last 4 weeks, with 2 assessments and 3 brief counseling sessions (Figure 2). Participants will be enrolled in the study once they have completed the baseline survey. Treatment will entail brief cessation counseling over the telephone or Zoom conferencing tool per participants' preferences, provision of written cessation materials (i.e., NCI's Clearing The Air booklet),⁹² and nicotine replacement therapy (NRT) in the form of nicotine patch and its instructions (e.g., suggested areas of body to put on) sent via mail; and brief mindfulness strategies/meditations delivered one-week pre-quit and 2 weeks post-quit. The mailout will also include instructions on how to use the app, and details about the study timeline. Meditations will continue 3 weeks post-quit.

Following the phone screen, eligible individuals will provide verbal informed consent and will be scheduled for the 1st counseling session. Baseline measures will be sent via REDCap to be completed online prior to the 1st session, during which participants will be oriented to the app for mindEMI and EMAs. The quit date (QD) will be scheduled for within about one week after the 1st session.

-14 (QD-2W) +21 (QD+3W) +84 (QD+12W) Day -7 (QD-1W) +14 (QD+2W) +/ (QD+1W) (QD) Intervention MBI delivered via Smartphone app Nicotine Replacement Therapy 2nd Brief Counsel 3rd Brief Counsel 1st Brief Counsel Assessment Baseline End of Tx FollowUp Ax [ROO phase only **Ecological Momentary Assessment** Figure 2. Study 2b Participant Flow of mindEMI (Note. QD = Quit Date, W = Week, Ax = Assessment, Tx = Treatment)

The 2nd session will occur around the QD and the 3rd session will take place approximately at the end of treatment (i.e., mindEMI; QD+2W).

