7. STATISTICAL CONSIDERATIONS

7.1. Sample Size/Accrual Rate

Aim 1. Aim 1 will recruit 15-20 cancer survivors who smoke for analyses. We will use an inductive thematic saturation approach, whereby interviews will continue until saturation is met, when no more new information (i.e., the number of new themes) is obtained. The thematic analysis literature recommends the sample size of 6 to 16. Thus, our sample will be 15-20 participants for analyses. Accounting for a drop out rate of ~30%, we will consent 26 participants. [name] will lead the qualitative analysis while consulting with [name] who has expertise in this area; resources available at Moffitt for qualitative analysis will also be used.

Aim 2. Aim 2 will consist of 10 cancer survivors who smoke, independent from Aim 1, to pilot the prototype mindfulness-based ecological momentary intervention (mindEMI). Recommended sample size in usability studies is at least N=10 to capture 94.7% of potential usability problems, which guided the current sample size, accounting for 30% drop out with a desired final sample size of 10 (will recruit N=13).

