7.2. Data Analysis

Aim 1. Two approaches of qualitative analysis will be used. First, the transcripts will be coded and key themes will be identified by 2 trained study staff. Texts will be analyzed for frequency (number of times the comment was mentioned), extensivity (number of participants making the comment), intensity (expressive strength of the comments), and specificity (degree of clear focus of the comment). A software, NVivo will be used to analyze the data. Coder agreement will be assessed using a Kappa statistic (\geq .80). Second, based on the principles of saturation in qualitative research, details of narratives will also be a focus of analyses. Qualitative analytic strategies such as immersion-crystallization will be implemented, in which the researcher reviews the data both intuitively and reflectively until the most relevant theme to the research questions arises. Descriptive analyses will be conducted on the data collected through survey and chart abstraction (M, SD, %).

Aim 2. The primary outcomes will be participants' open-ended feedback, and perceived utility and likability of the mindEMI based on the Aim 1 benchmarks and retention (\geq 75% through end of treatment). [name] will lead the qualitative thematic content analyses of the feedback and conduct descriptive analyses on usability measures (M, SD, %).

REFERENCES

1. US Department of Health and Human Services: Smoking Cessation: A report of the Surgeon General. Atlanta, GA, U.S. Department of Health and Human Services, Centers for Disease Control and Prevention, National Center for Chronic Disease Prevention and Health Promotion, Office on Smoking and Health, 2020

2. US Department of Health and Human Services: The health consequences of smoking—50 years of progress: a report of the Surgeon General, US Department of Health and Human Services, Centers for Disease Control and Prevention, National Center for Chronic Disease Prevention and Health Promotion, Office on Smoking and Health. Atlanta, GA, 2014

3. National Cancer Institute (NCI): Cancer survivors and smoking, 2018

4. Jassem J: Tobacco smoking after diagnosis of cancer: Clinical aspects. Transl Lung Cancer Res 8:S50, 2019

5. Guimond A-J, Croteau VA, Savard M-H, et al: Predictors of smoking cessation and relapse in cancer patients and effect on psychological variables: An 18-month observational study. Ann Behav Med 51:117-127, 2017

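### Aim 2's 30% dropout, its 13-to-10 head count (a 23% loss) and its 75% retention benchmark are not reconciled

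*Combined protocol and SAP*

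**What the plan says.** For Aim 2, section 7.1 gives the sample size as "accounting for 30% drop out with a desired final sample size of 10 (will recruit N=13"), and section 3.2.1 repeats the statement. Neither section gives the period over which the 30% is counted or the group it is a percentage of.

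Section 7.2 lists the Aim 2 primary outcomes: "The primary outcomes will be participants' open-ended feedback, and perceived utility and likability of the mindEMI based on the Aim 1 benchmarks and retention". The retention threshold is at least "75% through end of treatment". Section 1 also names retention among the primary outcomes, without a threshold: "perceived utility and likability of the mindEMI and retention through the end of treatment".

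Section 4.2.2 places enrolment after the phone screen and verbal consent: "Participants will be enrolled in the study once they have completed the baseline survey". No section says whether retention is a percentage of those consented, those enrolled, or those who started treatment.

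No hypothesis test or pass/fail rule is attached to retention. The Aim 2 analysis is thematic and descriptive.

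**The concern.** Three loss figures can be read from the Aim 2 text: 30% as stated, 23% from the head count in the same sentence, and at most 25% from the retention benchmark. If all three describe loss over the treatment period among the same people, they cannot all be what the sponsor is planning for.

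Two things are at stake. First, 13 recruits do not deliver the stated final 10 at the stated dropout. Second, a result such as 9 of 13 (69.2%) could be reported as in line with the planned dropout or as a miss on a primary-outcome benchmark, with nothing in the plan to settle which. Section 1 ties the showing of feasibility and acceptability benchmarks to a later, larger trial, so how such a result is described has some practical weight.

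**Working it through.** **Inputs.** Dropout 30%, final sample 10, number recruited 13 (sections 3.2.1 and 7.1). Retention benchmark at least 75% (section 7.2).

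**1. Reproduce the plan's 13.**
- Multiplying up: 10 x (1 + 0.30) = 13. This gives the stated figure exactly.
- Dividing by the proportion kept: 10 / (1 - 0.30) = 14.3, so 15 recruits would be needed for an expected final sample of at least 10.

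Aim 1 shows the same pattern: 20 x 1.3 = 26, the number to be consented in section 7.1.

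**2. What 13 recruits deliver.**
- Expected completers at 30% loss: 13 x 0.70 = 9.1.
- Loss implied by 10 of 13: 3/13 = 23.1%, or 76.9% retention.

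**3. What the benchmark needs with 13 in the denominator.**
- 0.75 x 13 = 9.75, so 10 completers are required.
- 10/13 = 76.9% meets it; 9/13 = 69.2% does not.

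A fourth loss therefore misses both the benchmark and the final sample of 10.

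**4. Chance of meeting the benchmark with 13.** Take completers X as binomial (13, p), an assumption that treats participants as independent with a common retention probability. At p = 0.70:

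- P(X = 10) = 286 x 0.70^10 x 0.30^3 = 0.218
- P(X = 11) = 78 x 0.70^11 x 0.30^2 = 0.139
- P(X = 12) = 13 x 0.70^12 x 0.30 = 0.054
- P(X = 13) = 0.70^13 = 0.010
- Sum: P(X >= 10) = 0.42, so P(miss) = 0.58

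The documents do not give an expected on-study retention, so the range matters:

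| True retention | P(at least 10 of 13) |
|---|---|
| 70% | 0.42 |
| 75% | 0.58 |
| 76.9% | 0.65 |
| 80% | 0.75 |
| 85% | 0.88 |
| 90% | 0.97 |

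**5. Would recruiting 15 settle it?** At a true 70%, the chance of at least 10 completers rises from 0.42 to 0.72. The benchmark would then need 12 of 15 (0.75 x 15 = 11.25), and the chance of that is 0.30. A larger sample repairs the head count but does not bring a 30% loss into line with a 75% benchmark.

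**6. Does the denominator matter?** Yes. As an illustration, suppose 13 consent, 12 complete the baseline survey and 9 reach end of treatment. The loss from consent is 4/13 = 30.8%, yet retention among those enrolled is 9/12 = 75%, which meets the benchmark. Under that reading the 30% and the 75% can stand together, although the final sample would be 9, not 10.

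**The case against.** A reader might go further and infer that the plan's own assumption forecasts a failed primary outcome. The documents do not support that, for these reasons:

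- An allowance for recruitment is not a forecast. The same 1.3 multiplier appears in both aims and looks like a general margin. Recruiting against a pessimistic loss while aiming for better retention is ordinary practice, and section 4.2.2 describes active retention efforts.
- The 30% may include people lost before enrolment. In Aim 1, section 7.1 applies a rate of about 30% to consented participants for a single interview, where loss would fall mainly between consent and interview. Aim 2 speaks of recruiting rather than consenting, so this is suggestive, not proof.
- The head count in the plan, 10 of 13, is 76.9% and meets the benchmark. Even at a true 70% the benchmark is met 42% of the time.
- Retention is one of several descriptive primary outcomes. Utility and likability carry the Aim 1 benchmark, also 75%, and nothing states what follows from a miss.

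All of this stands against the stronger inference. It leaves the head count untouched: whatever the 30% covers, 13 less 30% is 9.1, not 10. It also shows that a reader must guess what the 30% and the 75% are percentages of.

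**Conclusion.** The point holds as an inconsistency among stated figures. The 30% and the 13-to-10 head count contradict each other within one sentence: 30% leaves 9.1, while 10 of 13 is a 23.1% loss. This rests on arithmetic alone.

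The conflict with the benchmark is conditional. If the 30% means loss through end of treatment among the same 13 people, it implies 70% retention, 5 percentage points under the threshold, with about a 42% chance of meeting it under the binomial assumption. If it is a cautious margin or includes losses before enrolment, there need be no conflict. The documents do not say which is meant.

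The matter is modest in size. It does not undermine a descriptive usability pilot, but it should be corrected before results are seen.

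**What to change.** **Sections 3.2.1 and 7.1.** Keep N = 13 and replace the 30% dropout phrase with: *allowing for loss of at most 3 of 13 (23%)*. That yields the final sample of 10 and agrees with the 75% benchmark. It describes what 13 recruits can absorb; it is not evidence that 23% is the likely loss. If the sponsor prefers to keep 30%, state instead that 13 recruits are expected to leave about 9 completers.

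**Section 7.2.** State the retention denominator: participants enrolled at the baseline survey, or whichever group the sponsor intends. Report any loss between consent and enrolment separately.

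**Cost.** Wording in three places and no additional participants. The downside is that the stated attrition allowance becomes less generous or, if 30% is kept, that the plan concedes an expected final sample just under 10.
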